2.6 Correlative Studies Background

Our collaborative team recently completed a pilot study at Weill Cornell Medicine aimed at assessing the safety, clinical efficacy, and microbial engraftment of single FMT delivery by colonoscopy for active UC¹⁸. We performed a single-center, prospective, open-label pilot study to evaluate the safety and efficacy of two-donor fecal microbiota preparation (FMP) delivery by colonoscopy. The primary outcome was clinical response at week 4 with secondary endpoints including clinical remission, mucosal healing at week 4 and safety profile. Overall, 34 patients were screened, and 20 patients were enrolled. Seven patients (35%) achieved a clinical response (Mayo score ≥ 3 and a bleeding subscore ≤ 1) by week 4. Three patients (15%) were in clinical remission at week 4 (Mayo score ≤ 2 and no subscore > 1), and two of these patients (10%) achieved mucosal healing (endoscopy subscore of 0). Paired analysis showed a significant improvement in Mayo score (Median decrease of 1.5, $p = 0.03$) and endoscopic subscore (Median decrease of 0.5, $p = 0.002$). The present will test the hypothesis that prebiotic supplementation with psyllium will increase that clinical response rate over FMT alone. Furthermore, the current study will assess additional impact on clinical and endoscopic remission rates as well as placebo FMT.

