4.2 Inclusion Criteria

1. Male or Female \geq 18 years of age.
2. Documentation of prior history of mild to moderate UC.
3. Endoscopy confirmed active UC \geq 15 centimeters at day 0 screening colonoscopy.

- a. As defined by a total Mayo scoring of 4-10 with an endoscopic sub-score ≥ 1 and a stool frequency or rectal bleeding sub-score of ≥ 1 .
4. Patients must have a descending intact colon.
5. Patients taking steroid or biologic therapy must be on a stable dose for 4 weeks prior to screening and maintained throughout the trial.
6. Eligible patients willing to undergo serological and fecal screening testing prior to FMT to document baseline status:
 - a. Urine Testing
 - i. Pregnancy test (women with childbearing potential)
 - b. Blood Testing
 - i. B-HCG (research purposes)
 - ii. CBC, ESR, CRP, and BMP (standard of care)
 - iii. HIV, type I and II (standard of care)
 - iv. Hepatitis A B C Profile (standard of care)
 - v. RPR (*treponema pallidum*) (research purposes)
 - vi. CMV IgM (standard of care)
 - vii. Quantiferon-TB (standard of care)
 - c. Stool Testing
 - i. Calprotectin (standard of care)
 - ii. Clostridium Difficile Toxin PCR (standard of care)
 - iii. Ova & parasites (standard of care)
 - iv. Gastrointestinal Pathogen PCR Panel (standard of care)
 1. *Campylobacter* species
 2. *Plesiomonas Shigelloides*
 3. *Salmonella* Species
 4. *Vibrio* Species
 5. *Vibrio cholerae*
 6. *Yersinia Enterocolitica*
 7. Enterotoaggregative *E. coli* (EAEC)
 8. Enteropathogenic *E. coli* (EPEC)
 9. Enterotoxigenic *E. coli* (LT/ST)
 10. Shigalike toxin producing *E.coli* I (STX/ST2)
 11. *Cryptosporidium*
 12. *Cyclospora cayetanensis*
 13. *Entamoeba cayetanensis*
 14. *Giardia*
 15. *Adenovirus* F 40/41
 16. *Astrovirus*
 17. *Norovirus* GI/GII
 18. *Rotavirus* A
 19. *Sapovirus*
 20. *GID* PCR INTERP

7. Patients must discontinue anti-rCDI antibiotics (e.g. vancomycin, fidaxomicin) 48 hours prior to FMT delivery procedure.

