10.1 Response Criteria

10.1.1 Primary Endpoint Assessments

10.1.1.1 Mayo Scoring System³⁰

The Mayo Scoring System will be used for the assessment of ulcerative colitis activity. It is a composite score that ranges from 0-12 based on the following four categories: bleeding, stool frequency, physician assessment, and endoscopic findings. A partial Mayo Score ranges from 0-9 and can also be utilized if no endoscopic visualization is available to assess disease activity.

Study subjects will be evaluated by a full Mayo score at day 0 and week 8, and a partial Mayo score at the week 4 clinic visit. Both clinical response and remission will be evaluated at week 8 post-FMT. Clinical response is described as a reduction of the Mayo score by >3 points and >30% reduction from baseline with an accompanying decrease in the sub-score for rectal bleeding of at least 1 point. Clinical remission will be defined by Mayo score \leq 2 without any sub-score >1, and Mayo endoscopic sub-score 0-1.

Table 2. Mayo Scoring System for the assessment of ulcerative colitis activity.

Stool frequency [†]
0 = Normal no. of stools for this patient
1 = 1 to 2 stools more than normal
2 = 3 to 4 stools more than normal
3 = 5 or more stools more than normal
Subscore, 0 to 3
Rectal bleeding [‡]
0 = No blood seen
1 = Streaks of blood with stool less than half the time
2 = Obvious blood with stool most of the time
3 = Blood alone passes
Subscore, 0 to 3
Findings on endoscopy
0 = Normal or inactive disease
1 = Mild disease (erythema, decreased vascular pattern, mild friability)
2 = Moderate disease (marked erythema, lack of vascular pattern, friability, erosions)
3 = Severe disease (spontaneous bleeding, ulceration)
Subscore, 0 to 3
Physician's global assessment [§]
0 = Normal
1 = Mild disease
2 = Moderate disease
3 = Severe disease
Subscore, 0 to 3

* The Mayo score ranges from 0 to 12, with higher scores indicating more severe disease. Data are from Schroeder et al.²⁴

† Each patient serves as his or her own control to establish the degree of abnormality of the stool frequency.

‡ The daily bleeding score represents the most severe bleeding of the day.

§ The physician's global assessment acknowledges the three other criteria, the patient's daily recollection of abdominal discomfort and general sense of well-being, and other observations, such as physical findings and the patient's performance status.

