12.4 Analysis of Endpoints

12.4.1 Analysis of Primary Endpoints

1. Clinical response at week 8 post-FMT, as defined by the reduction of the Mayo scoring system by >3 points (+30% reduction) with an accompanying decrease in the sub-score for rectal bleeding of at least 1 point (Section 10.1.2.2).

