13.2.4 Protocol-Specific Exceptions to SAE Reporting

A suspected clinical endpoint event, regardless of when the event occurs, is not to be reported as an AE or SAE or reported in an expedited manner as an SAE. The suspected clinical endpoint event includes:

- Recurrent UC flare
- Initial response to therapy with initial reduction to Mayo score ≤ 3 with an accompanying decrease in the sub-score for rectal bleeding of at least 1 point or an absolute sub-score for rectal bleeding of 0 or 1

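### The >3-point response rule requires a fall of at least 4 on the integer Mayo score, so the 30% clause never acts and some patients entering at 4 or 5 are in remission yet fail the primary endpoint

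*Combined protocol and SAP*

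**What the plan says.** Section 10.1.1.1 defines the primary endpoint: "Clinical response is described as a reduction of the Mayo score by >3 points and >30% reduction from baseline". A further condition is that the bleeding sub-score drops by 1 or more. Section 12.4.1 gives the same points threshold, "reduction of the Mayo scoring system by >3 points (+30% reduction", with a plus sign where 10.1.1.1 has a greater-than sign. It refers the reader to 10.1.2.2, which is the adverse event reporting section.

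On the scale, 10.1.1.1 states: "It is a composite score that ranges from 0-12 based on the following four categories". Table 2 scores each category 0, 1, 2 or 3. On entry, 4.2 states: "As defined by a total Mayo scoring of 4-10", with an endoscopic sub-score of at least 1 and a stool frequency or bleeding sub-score of at least 1. Remission (10.1.1.1, 12.4.2) is a total of 2 or less with no sub-score above 1.

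Response is worded differently in two other places. For the pilot, 2.2 and 2.6 report "Seven patients (35%) achieved a clinical response" at week 4 and give the rule as a Mayo figure of ≥ 3 (read here as a fall of 3 or more) with a bleeding sub-score of 1 or less. Section 13.2.4 has "Initial response to therapy with initial reduction to Mayo score" of 3 or less, and accepts either a bleeding fall of 1 or an absolute bleeding sub-score of 0 or 1.

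**The concern.** A threshold of more than 3 on a whole-number score is a threshold of 4. That does not fit the rest of the plan. The percentage condition has nothing left to do, which suggests that the written threshold may not be the intended one. The mildest patients admitted by 4.2 must lose every point to count as responders. Some patients can succeed on the secondary endpoint of remission and fail the primary endpoint of response, although remission would normally be the harder target.

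At stake is the classification of individual patients on the primary endpoint. It is also unclear whether the planning rates in 12.1 refer to the endpoint that will be analysed.

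**Working it through.** **Planned power (12.1).** Inputs: 55% v 27%, 45 per arm, two-sided 0.05, stated power about 80%. The pooled rate is 0.41.
- SE under the null: √(2 × 0.41 × 0.59 / 45) = 0.1037
- SE under the alternative: √((0.55 × 0.45 + 0.27 × 0.73) / 45) = 0.0994
- Power: Φ((0.28 − 1.96 × 0.1037) / 0.0994) = Φ(0.772) = 78.0%

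The stated figure is reproduced to within 2 points.

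**Percentage clause.** For each eligible baseline B, the smallest qualifying percentage fall is 4/B under >3 and 3/B under at least 3.

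| Baseline | Highest week 8 score that qualifies under >3 | 4/B | 3/B |
|---|---|---|---|
| 4 | 0 | 100% | 75% |
| 5 | 1 | 80% | 60% |
| 6 | 2 | 66.7% | 50% |
| 7 | 3 | 57.1% | 42.9% |
| 8 | 4 | 50% | 37.5% |
| 9 | 5 | 44.4% | 33.3% |
| 10 | 6 | 40% | 30% |

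Under >3 every value in the 4/B column exceeds 30%. Even at a total of 12, 4/12 = 33.3%. The clause therefore changes no classification. Under a 3-point rule a strict >30% acts once, for 10 to 7 (exactly 30%), and a clause of at least 30% acts nowhere from 4 to 10.

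**Remission without response.** Two examples, with sub-scores in the order stool frequency, bleeding, endoscopy, physician's assessment:
- (1,1,1,1) to (0,0,1,0): total 4 to 1, a 75% fall, bleeding down 1, in remission. The fall is 3, so not a responder.
- (1,1,2,1) to (1,0,1,0): total 5 to 2, a 60% fall, bleeding down 1, in remission. The fall is 3, so not a responder.

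The last step enumerates every eligible baseline pattern against every remission pattern, keeping pairs in which bleeding falls by at least 1 and no sub-score worsens.

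| Baseline | Transitions into remission | Response under >3 | Response under at least 3 |
|---|---|---|---|
| 4 | 47 | 10 | 32 |
| 5 | 106 | 65 | 106 |
| 6 or more | all | all | all |

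At baseline 4 the 47 transitions end at 0 (10), 1 (22) or 2 (15). The 15 that end at 2 are falls of 2, so they still fail under a 3-point rule. From baseline 6 up, any remission is a fall of at least 4. These are counts of possible score patterns, not of patients.

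**Power, as illustration only.** Suppose the 55% and 27% were rates under a 3-point rule and a share s of those responders in each arm fell by exactly 3. The rates become 0.55(1 − s) and 0.27(1 − s). Exact binomial power of the uncorrected chi-square test, 45 per arm:

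| s | Rates | Power |
|---|---|---|
| 0 | 55 / 27% | 78% |
| 10% | 49.5 / 24.3% | 71% |
| 20% | 44 / 21.6% | 64% |
| 30% | 38.5 / 18.9% | 56% |

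The documents support neither the supposition nor the values of s.

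**The case against.** The two operative definitions, in 10.1.1.1 and 12.4.1, agree on >3 points, and a stricter threshold than an open-label pilot's is a permissible choice. Section 13.2.4 lists events exempt from adverse event reporting and does not define the endpoint. Both points stand. They do not explain a percentage clause that can never act, or a primary endpoint that some remitters fail.

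A reader might infer that the trial loses power. The documents do not support that. Section 12.1 attributes the 27% to prior studies and clinical experience. Section 2.2 gives 27% as another trial's primary outcome, without its definition. The pilot's rate was 35% at week 4. Section 12.1 cites the pilot for the approximate doubling to 55%, but the pilot as described had no fiber arm. Nothing shows that the planning rates follow a 3-point rule, and no share of exact 3-point falls is given.

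A reader might also infer bias between arms. The rule is the same in both, so there is none from this source.

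Nor does a 3-point rule remove every conflict with remission, since 4 to 2 remains. The bleeding condition is a separate cause: 4.2 admits patients on stool frequency alone, and a patient with a bleeding sub-score of 0 at entry (32 of 166 eligible score patterns) cannot respond at any points threshold.

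**Conclusion.** The point holds as a defect in the primary endpoint definition. It follows from the plan's own definitions that response needs a fall of at least 4, that the 30% clause is inert across the entry range, that a patient entering at 4 must reach 0, and that 4 to 1 and 5 to 2 can be remission and primary failure together.

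Its reach is limited. The conflict with remission that comes from the points threshold exists only at baselines 4 and 5, and the number of patients affected depends on an enrolment mix that the documents do not give. The comparison of FMT plus fiber with FMT alone is not biased by it, and no loss of power can be stated. The definition still has to be settled, because it decides individual classifications on the primary endpoint and differs from the pilot rule in work that 12.1 cites.

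**What to change.** Before unblinding, in 10.1.1.1 and 12.4.1:

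1. State *a reduction of at least 3 points*. Then either keep a strict *>30%*, knowing that it acts only for 10 to 7, or delete the percentage clause. Do not write *at least 30%*, which would exclude nobody at baselines 4 to 10.
2. Because 4 to 2 would still be remission without response, state how a subject who meets remission but not the points rule is classified for response.
3. If a 4-point fall is intended, say so explicitly and delete the percentage clause. State which response definition the 27% and 55% planning rates assume.
4. Reconcile the response wording in 13.2.4 with the chosen definition, and correct the cross-reference in 12.4.1 to 10.1.1.1.

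The change needs no new data, visits or patients, because the full Mayo score is already recorded at day 0 and week 8. It is more than an editorial correction, though. The synopsis gives enrolment as 2019-2023, so a changed threshold may be an amendment to the primary endpoint after enrolment has begun. It would need a recorded reason and the ethics approval described in 11.2.1. After unblinding the same change would look data-driven.

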10.1.2 Secondary Endpoint Assessments

10.1.2.1 Biomarkers

Blood, stool, and mucosal samples will be processed and analyzed in the [name] Laboratory. The schedule and frequency of these collections are present in the Table of Events (Table 1). The total amount of blood collected for biomarker and safety evaluations will be specified in the Informed Consent Form.

10.1.2.2 Adverse Event Reporting

See Section 13 for more information on AE and/or SAE reporting for safety evaluation.

10.2 Duration of Response

Not applicable.

10.3 Progression-Free Survival

Not applicable.

10.4 Other Response Parameters

See Section 12.4 for a description of all other study endpoints.

11. Data Reporting / Regulatory Considerations

11.1 Data Collection

The data collection plan for this study is to utilize REDCap to capture all treatment, toxicity, efficacy, and adverse event data for all enrolled subjects.

11.1.1 REDCap

REDCap (Research Electronic Data Capture) is a free data management software system that is fully supported by the Weill-Cornell Medical Center CTSC. It is a tool for the creation of customized, secure data management systems that include Web-based data-entry forms, reporting tools, and a full array of security features including user and group-based privileges, authentication using institution LDAP system, with a full audit trail of data manipulation and export procedures. REDCap is maintained on CTSC-owned servers that are backed up nightly and support encrypted (SSL-based) connections. Nationally, the software is developed, enhanced and supported through a multi-institutional consortium led by the Vanderbilt University CTSA.

11.2 Regulatory Considerations

11.2.1 Institutional Review Board/Ethics Committee Approval

As required by local regulations, the Investigator will ensure all legal aspects are covered, and approval of the appropriate regulatory bodies obtained, before study initiation.

Before initiation of the study at each study center, the protocol, the ICF, other written material given to the patients, and any other relevant study documentation will be submitted to the appropriate Ethics Committee. Written approval of the study and all relevant study information must be obtained before the study center can be initiated or the IP is released to the Investigator. Any necessary extensions or renewals of IEC/IRB approval must be obtained for changes to the study, such as amendments to the protocol, the ICF, or other study documentation. The written approval of the IEC/IRB together with the approved ICF must be filed in the study files.

The Investigator will report promptly to the IEC/IRB any new information that may adversely affect the safety of the patients or the conduct of the study. The Investigator will submit written summaries of the study status to the IEC/IRB as required. On completion of the study, the IEC/IRB will be notified that the study has ended.

Neither the Investigator nor BMS will modify or alter this protocol without the agreement of the other. All agreed protocol amendments will be clearly recorded on a protocol amendment form and will be signed and dated by the original protocol approving signatories. All protocol amendments will be submitted to the relevant institutional IEC/IRB for approval before implementation, as required by local regulations. The only exception will be when the amendment is necessary to eliminate an immediate hazard to the trial participants. In this case, the necessary action will be taken first, with the relevant protocol amendment following shortly thereafter.

Once protocol amendments or consent form modifications are implemented at the lead site, Weill Cornell Medicine, updated documents will be provided to participating sites. Weill Cornell Medicine must approve all consent form changes prior to local IRB submission.

Relevant study documentation will be submitted to the regulatory authorities of the participating countries, according to local/national requirements, for review and approval before the beginning of the study. On completion of the study, the regulatory authorities will be notified that the study has ended.

11.2.2 Ethical Conduct of the Study

The Investigators and all parties involved should conduct this study in adherence to the ethical principles based on the Declaration of Helsinki, GCP, ICH guidelines and the applicable national and local laws and regulatory requirements.

This study will be conducted under a protocol reviewed and approved by the applicable ethics committees and investigations will be undertaken by scientifically and medically qualified persons, where the benefits of the study are in proportion to the risks.

11.2.3 Informed Consent

The investigator or qualified designee must obtain documented consent according to ICH-GCP and local regulations, as applicable, from each potential subject or each subject's legally authorized representative prior to participating in the research study. Subjects who agree to participate will sign the approved informed consent form and will be provided a copy of the signed document.

The initial ICF, any subsequent revised written ICF and any written information provided to the subject must be approved by IRB prior to use. The ICF will adhere to IRB/IEC requirements, applicable laws and regulations.

11.2.4 Compliance with Trial Registration and Results Posting Requirements

Under the terms of the Food and Drug Administration Modernization Act (FDAMA) and the Food and Drug Administration Amendments Act (FDAAA), the Sponsor-Investigator of the trial is solely responsible for determining whether the trial and its results are subject to the requirements for submission to <http://www.clinicaltrials.gov>. Information posted will allow subjects to identify potentially appropriate trials for their disease conditions and pursue participation by calling a central contact number for further information on appropriate trial locations and trial site contact information.

11.2.5 Record Retention

Essential documents are those documents that individually and collectively permit evaluation of the study and quality of the data produced. After completion of the study, all documents and data relating to the study will be kept in an orderly manner by the Investigator in a secure study file. Essential documents should be retained for 2 years after the final marketing approval in an ICH region or for at least 2 years since the discontinuation of clinical development of the IP. In addition, all subjects' medical records and other source documentation will be kept for the maximum time permitted by the hospital, institution, or medical practice.

12. Statistical Considerations

12.1 Sample Size and Analysis Plan

Prior studies and clinical experience involving FMT suggests a 27% response rate from a null rate of diet alone at 7%. Based on previous work¹⁸, we estimate the effect size of clinical response to FMT+fiber in patients with IBD to be approximately double the FMT-alone group (i.e., 55% vs. 27%, respectively). Recruitment of ~135 subjects with 45 patients per arm was calculated assuming a 55% response rate at 8 weeks in the FMT+fiber arm and a 27% response rate at 8 weeks in the FMT-alone arm, with approximately 80% power to detect this difference (using a two-sided significance level of 0.05)³¹. We will conduct pairwise chi-square analysis between the study arms of interests to directly address the primary study objective to detect a difference in clinical response (i.e. FMT+ fiber versus FMT alone). The remaining two pairwise comparisons can be considered as secondary aims and thus no multiple comparison adjustment is needed.

Considering analyses will be performed based on intent to treat, any subject in the FMT alone (no psyllium) or the FMT with psyllium intervention groups with missing primary endpoint data at week 8 will be labeled as failed treatment (no change in clinical response from baseline). Therefore, subjects with missing data will have their baseline Mayo score carried forward to remain the same for the week 8 primary endpoint. For primary efficacy analysis, the populations FMT + psyllium vs. FMT alone (no fiber) will be compared by the chi-square test (pair-wise group comparisons will also be performed). Those characteristics found to be clinically different between groups at baseline using significance criteria of $p < 0.05$ or known to be clinically important (e.g., in the event randomization provided insufficient balance between groups) will be incorporated into a multivariable logistic regression model of clinical response (i.e., binary outcome variable). This will facilitate estimating the independent effect of treatment group status on clinical response, after controlling for such factors, if any, that may differ between the two study arms at baseline. Sensitivity analyses for the primary endpoint will also be performed; in addition to carrying forward the baseline Mayo score for subjects with missing data at week 8, the minimum, median, and maximum Mayo score of subjects with available data at week 8 will be used (imputed) for subjects with missing data at week 8. Similarly, we will also explore multiple imputation techniques under varying assumptions of missingness (e.g., missing completely at random and missing at random). These multiple imputation techniques will rely on regression models to predict the missingness and missing values, and incorporate uncertainty through an iterative approach. For dealing with the possibility of data not missing at random, a worst-case analysis will be explored (i.e., missing data are replaced with the “worst” value under the not missing at random [non-ignorable] assumption). These sensitivity analyses will allow for an assessment of the consistency of the primary endpoint difference between groups under the varying assumptions for missing data at week 8.

Similar analyses will be conducted for secondary and exploratory endpoints (i.e., need for escalation, clinical remission, etc.). For secondary efficacy and safety analysis, comparison populations include: (i) FMT alone (no fiber) vs. placebo FMT alone (no fiber); (ii) FMT (with or without fiber) vs. placebo FMT (with or without fiber); (iii) placebo FMT with fiber vs. placebo FMT alone (no fiber); (iv) FMT with fiber vs. placebo FMT with fiber. All p-values will be two-sided with statistical significance evaluated at the 0.05 alpha level. Ninety-five percent confidence intervals for all parameters of interest will be calculated to assess the precision of the obtained estimates. Secondary analysis excluding subjects who discontinued the study treatment for reasons clearly not related to the study medications will also be performed. Treatment groups will be assessed at baseline with primary objective criteria. Balance between treatment groups will be assessed by ANOVA tests or Kruskal-Wallis tests for continuous variables and chi-square tests or Fisher’s exact tests for categorical variables.

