7.12 Measures to Minimize Bias: Randomization and Blinding

Randomization Bias:

A series of randomized blocks of fixed size will be generated with a 1:1:1 allocation ratio. This will provide assurance that after a given block as completed subject enrollment, there will be the same number of subjects assigned to each of the three study arms. Only the statistician and the study coordinator will have access to the randomization list. The dedicated research coordinator will assign the randomization code from the list for each subsequently enrolled patient (i.e., the statistician will give the list that contains the randomized blocks only to the research assistant).

Unblinding Bias:

Clinicians are blinded while they assess the clinical response at week 8 and will be unblinded only once all clinical evaluations at week 8 have been conducted for all 135 study participants. This will reduce the risk of potential bias by the clinician as all treatment groups will receive treatment (blinded investigational or placebo FMP250) at week 8 by flexible sigmoidoscopy.

Unblinding in the case of emergency (i.e. anticipated or unanticipated serious adverse event) is up to the discretion of the treating physician, particularly if it is medically necessary to know what treatment assignment the subject received. However, it is advised that the treating physician

discuss with the principal investigator prior to breaking protocol. The study coordinator will not delay or refuse unblinding if knowledge of the investigational drug is imperative for emergency treatment. The study coordinator will then immediately notify the PI of unblinding and will document the reason in the subject's folder and/or eCRF.

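### The supportive adjusted model for week 8 response takes its covariates from a baseline p < 0.05 test or an open clause, and no covariate is named in advance

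*Combined protocol and SAP*

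**What the plan says.** Section 12.1 sets the primary test: "For primary efficacy analysis, the populations FMT + psyllium vs. FMT alone (no fiber) will be compared by the chi-square test". It then adds a multivariable logistic model of clinical response, with two routes by which a covariate can enter:

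- **Route 1:** "Those characteristics found to be clinically different between groups at baseline using significance criteria of" p < 0.05.
- **Route 2:** "or known to be clinically important (e.g., in the event randomization provided insufficient balance between groups) will be incorporated into" the model.

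The stated aim is to estimate the treatment effect "after controlling for such factors, if any, that may differ between the two study arms at baseline".

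No section lists the covariates. The last paragraph of Section 12.1 says "Treatment groups will be assessed at baseline with primary objective criteria" and names the balance tests (ANOVA or Kruskal-Wallis, chi-square or Fisher). It does not name the variables or place any of them in the model. Section 12.3 has no stratification factors. On who can see allocation, Section 7.12 says "Only the statistician and the study coordinator will have access to the randomization list".

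**The concern.** A baseline significance test in a randomised trial asks whether chance produced a difference. Whether a covariate deserves adjustment depends on how strongly it predicts the outcome, and the test does not measure that. Route 1 therefore leaves prognostic variables out most of the time and occasionally lets irrelevant ones in.

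Route 2 could repair this, but it has no list and no timing, and its one example again depends on the imbalance observed. The statistician holds the randomization list, so blinding of the clinicians does not by itself show that covariates were chosen without sight of outcomes by arm.

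Two obvious candidates go unnamed although the endpoint is built from them. Response in Sections 10.1.1.1 and 12.4.1 requires a Mayo fall of more than 3 points and a rectal-bleeding fall of at least 1. Entry in Section 4.2 is "As defined by a total Mayo scoring of 4-10 with an endoscopic sub-score" of at least 1 "and a stool frequency or rectal bleeding sub-score of" at least 1, so a bleeding sub-score of 0 is allowed if stool frequency is at least 1. As worded, a subject entering with bleeding 0 cannot respond, and one entering at Mayo 4 must reach 0. What is at stake is how informative and how credible the supportive estimate is.

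**Working it through.** **Inputs from the plan.** 45 per arm; response 55% v 27%; two-sided 0.05 (Section 12.1). Full Mayo score at day 0 (Section 10.1.1.1). The plan gives neither the prevalence of bleeding 0 at entry nor the prognostic strength of any covariate, so both are assumed below.

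**The plan's own figure.** With unpooled variance, SE = sqrt((0.55×0.45 + 0.27×0.73)/45) = 0.0994, and power = Φ(0.28/0.0994 − 1.96) = 80.4%. With pooled variance it is 78.0%. The stated 80% reproduces. The covariate rule has no stated figure.

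**Route 1, chance of entry.** Each covariate enters with probability 0.05. For two independent covariates, at least one enters with probability 1 − 0.95² = 9.75%, so both are left out about 90% of the time. In simulation with correlated Mayo and bleeding scores, either one entered in 8-9% of trials.

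**Route 1, what goes unflagged.** The largest standardised difference that a two-arm t-test does not flag is t(0.975, 88) × sqrt(2/45) = 1.987 × 0.2108 = 0.419 SD. Section 12.1 names ANOVA. With three arms and the third midway, the limit is about 0.52 SD.

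**Precision.** Trials were simulated at 45 per arm, with sub-scores filtered to the Section 4.2 entry rule and 20% of subjects assumed to enter with bleeding 0. Four prognostic patterns were used: flat; odds ratio 0.74 per Mayo point; 1.35 per Mayo point; and 1.8 per bleeding point. Rates were 55 v 27% and 27 v 27%. The table gives the SD of the estimated risk difference against the unadjusted estimate.

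| Response definition | Arm + Mayo + bleeding, fixed | p < 0.05 route alone |
|---|---|---|
| As worded (bleeding 0 cannot respond) | 0.8-7.4% smaller | 0.1-3.1% smaller |
| Bleeding-0 subjects able to respond | about 1.5% larger to 2.5% smaller | about 0.4% larger to 1.1% smaller |

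For scale, the crude 95% half-width at the design rates is 1.96 × 9.94 = 19.5 percentage points, so the best gain in the table is 0.074 × 19.5 = 1.4 points.

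**A tail example, definition as worded.** Suppose 6 v 12 bleeding-0 subjects. Pooled prevalence is 18/90 = 0.20, z = (6/45)/sqrt(0.2×0.8×2/45) = 1.58 and p = 0.11, so a Pearson test does not flag it. With no treatment effect and 27% overall response, the rate among the others is 0.27/0.80 = 0.3375. The crude difference shifts by 0.3375 × 6/45 = 4.5 points. Unflagged imbalances of 6 or more occur in 9.2% of trials. The average imbalance is 3.0 subjects, worth 0.3375 × 3.0/45 = 2.3 points, against an SE of 9-10 points.

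**Type I error of the adjusted test.** In the same simulations (10, 20 and 30% bleeding 0), the fixed model rejected in 4.7-5.1% of null trials and the p < 0.05 route in 3.9-4.9%. Picking the smallest p among four models (none, Mayo, bleeding, both) after outcomes were known gave 5.9-7.7%.

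**Size of model.** Expected responders are 45 × (0.55 + 0.27) = 36.9 under the design rates, or 45 × 0.54 = 24.3 if both arms are at 27%.

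**The case against.** The strongest reply is that the p < 0.05 route is only half of the plan's rule. On an ordinary reading, the clinical-importance clause can admit baseline Mayo or bleeding, or an imbalance such as 6 v 12. This stands: the route 1 figures do not describe the whole rule, and the documents do not support saying that the adjusted estimate will usually equal the crude one. What the clause does not do is say which variables it covers or when they are chosen.

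Second, most of the precision gain and all of the 4.5-point shift come from bleeding-0 subjects being unable to respond. That is a separate conflict between eligibility and endpoint. Section 13.2.4 words response differently, accepting a low absolute bleeding sub-score as an alternative to a fall. These sections must be reconciled, and adjustment does not do that. This also stands, and the second row of the table shows how little gain remains.

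Third, a reader might infer that the rule inflates type I error. It does not: route 1 uses baseline data only. The 6-8% figure arises only if someone picks the smallest p after seeing outcomes. Nothing in the documents says that this will happen, and a model so chosen could not replace the chi-square as primary.

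Fourth, a reader might infer that the trial loses power. The planned power belongs to the chi-square test, which this point leaves alone.

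**Conclusion.** The concern holds as a minor point about a supportive analysis. The covariates are selected by a test unrelated to prognosis or by a clause with no list and no date, so the adjusted estimate is not pre-specified. The remedy is a better method than the stated rule and costs almost nothing.

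The statistical gain is modest and conditional. It is about 1-7% in SD if the response definition stays as worded and 20% enter with bleeding 0. It is close to nil, and possibly slightly negative, if bleeding-0 subjects can respond. Those ranges rest on assumed prevalence and prognostic strength. The lasting benefit is that a reader can see that the model was fixed before the result was known. The validity of the chi-square test, its error rate, the power and the sample size are not in question.

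**What to change.** In Section 12.1, replace the p < 0.05 trigger, the open clinical-importance clause and the closing condition that adjustment depends on observed differences. Put in their place one adjusted analysis of week 8 response, FMT + psyllium v FMT alone:

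- a logistic model with arm, baseline total Mayo score and baseline rectal-bleeding sub-score (0-3, numeric), fitted whatever the observed balance;
- reported as a standardised risk difference with a 95% CI from a robust (influence-function) standard error.

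Name any further covariate judged clinically important at the same time, and keep such additions few given about 24-37 responders. Calprotectin, CRP and steroid or biologic use are already recorded and could be considered. Date the text before unblinding; because the statistician holds the randomization list, that date is what shows the choice came first. The balance tests stay as description only, and the chi-square stays primary.

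**Cost.** Wording only, since both covariates are collected at day 0. The SD may be up to about 1.5% larger if the covariates prove non-prognostic. A numeric bleeding term avoids the empty responder category that a categorical term would have under the present definition. It corrects a bleeding-0 imbalance only in part, leaving 1.4-2.8 of the 4.5 points in the 6 v 12 example. The robust standard error is needed because plain delta-method intervals covered 92.9-94.1% in simulation, against 93.9-94.7% with it.
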